8.9 Withdrawal Criteria

It is the right and the duty of the investigator or subinvestigator to stop treatment in any case in which emerging effects are of unacceptable risk to the individual patient. In addition, the investigator or subinvestigator is to stop treatment of any patient with unmanageable factors that may interfere significantly with the trial procedures and/or the interpretation of results.

A patient must be discontinued from the study for any of the following reasons:

1. The patient fails to achieve remission by Week 6 or stability by Week 8 of the OL treatment period;

- 2. After stability criteria (Section 4.5) have been met, if there is a lack of ongoing stability as evidenced by an excursion event of YMRS total score of \geq 17 and/or MADRS total score of \geq 20, or CGI-S \geq 4;
- 3. The patient initiated treatment with a mood stabilizer, antidepressant, antipsychotic agent, or with a benzodiazepine that exceeds the protocol-specified allowance or duration (ie, more than 2 mg/d of lorazepam equivalent or for more than 3 consecutive days) to treat worsening mood symptoms;
- 4. The patient required or initiated hospitalization for his/her psychiatric symptoms (excluding the discretionary hospitalization stay which is to end no later than Visit 3 [Day 8] of the OL treatment period or extension of the initial hospitalization described in this protocol);
- 5. At the end of the OL treatment period, the patient does not meet all criteria to enter the DB treatment period (eg, patient is unable to tolerate cariprazine 3.0 mg/d);
- 6. Positive UDS after enrollment, confirmed by retest at next scheduled visit; for exceptions see Exclusion Criterion 6(b) and Section 4.8.3;
- 7. The patient meets the criteria for relapse of a mood episode during the DB treatment period;
- 8. The patient experiences 1 of the following elevated liver enzyme conditions, which is confirmed by repeat testing:
 - ALT or AST $> 3 \times$ ULN and total bilirubin $> 2 \times$ ULN,
 - ALT or AST $> 8 \times ULN$,
 - ALT or AST $> 5 \times ULN$ for more than 2 weeks,
 - ALT or AST > 3 × ULN with the appearance of jaundice, worsening of fatigue, nausea, vomiting, right upper quadrant pain or tenderness, fever, rash, or eosinophilia.
- 9. The patient has an absolute neutrophil count of < 1000 per mm³ and, after repeat testing within 24 hours of awareness, the values are not normalized or are not increasing;
- 10. A female patient becomes pregnant during treatment.

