9.0 EXTENT OF EXPOSURE AND TREATMENT COMPLIANCE**9.1 EXTENT OF EXPOSURE**

Exposure to the OL IP for the OL Safety Population will be summarized for treatment duration, calculated as the number of days from the date of the first dose of OL cariprazine taken to the date of the last dose taken during the OLTP, inclusive. Descriptive statistics (n, mean, standard deviation, median, Q1, Q3, minimum and maximum) will be presented.

Exposure to the DB IP for the DB Safety Population during the DBTP will be summarized for treatment duration, calculated as the number of days from the date of the first dose of DB IP to the date of the last dose of DB IP, inclusive. Descriptive statistics (n, mean, standard deviation, median, Q1, Q3, minimum, and maximum) will be presented by treatment group.

Exposure to cariprazine during the entire study (OLTP and DBTP) will be summarized by intervals for the OL Safety Population. Descriptive statistics (n, mean, standard deviation, median, Q1, Q3, minimum, and maximum) will be presented.

By design, patients will take a fixed dose of cariprazine and there is no titration period during the DBTP. Mean daily dose, final dose will not be provided during the DBTP.

Patient-years, defined as exposure to the IP in years, will be summarized for the OLTP for the OL Safety Population. Patient-years will also be summarized by treatment group for the DBTP for the DB Safety Population. Patient years of exposure to cariprazine during the entire study (OLTP and DBTP) will also be summarized for the OL Safety Population.

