11.1 ADVERSE EVENTS

Aes will be coded by system organ class and preferred term using the *Medical Dictionary for Regulatory Activities* (MedDRA), Version 21.0 or newer.

An AE will be considered a treatment-emergent adverse event (TEAE) if the AE began or worsened (increased in severity or became serious) on or after the date of the first dose of OL IP. Per eCRF instructions, a new AE record will be created with a new AE onset date for any AE that worsens. Therefore, TEAEs can simply be identified as those Aes with recorded onset date (and time, if known) on or after the date of the first dose of IP.

The number and percentage of patients reporting TEAEs during the OLTP will be tabulated by system organ class and preferred term; by system organ class, preferred term, and severity; and by system organ class, preferred term, and relationship to IP.

The number and percentage of patients reporting TEAEs during the DBTP will be tabulated for each treatment group by system organ class and preferred term; by system organ class, preferred term, and severity; and by system organ class, preferred term, and relationship to IP. The total number and percentage of TEAEs during the DBTP will also be summarized by severity and relationship to IP for each treatment group.

The number and percentage of patients reporting TEAEs during the OL SFU period will be tabulated by system organ class and preferred term for the OL Safety Population. The number and percentage of patients reporting TEAEs during the DB SFU period will be tabulated by system organ class, preferred term, and DB treatment group for the DB Safety Population.

For OLTP, DBTP, or SFU period, if more than 1 AE was coded to the same preferred term for the same patient, the patient will be counted only once for that preferred term using the most severe and most related occurrence for the summarization by severity and by relationship to IP.

An AE that occurs more than 30 days after the date of the last dose of DB IP or occurs after the last SFU visit (whichever comes last) will not be summarized except for Aes related to reported pregnancies. Aes associated with pregnancies reported in the protocol-required timeframe up to approximately 12 weeks following the last dose of DB IP will be summarized.

The number and percentage of patients with common ($\geq 2\%$ of patients in any treatment group) TEAEs will be summarized by preferred term for OLTP and be summarized by preferred term and treatment group for DBTP.

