14.0 DETERMINATION OF SAMPLE SIZE

The sample size and power calculations are based on the analysis of time to relapse of any mood episode in the DBTP to compare each cariprazine dose group versus placebo-based on a log-rank test. The trial will be a fixed follow-up design. Patients are followed from randomization until dropout, relapse or a fixed duration of 39 weeks.

The relapse HR is assumed to be 0.42 based on cariprazine maintenance study in patients with schizophrenia ([Durgam 2016](#)) [REDACTED] compounds (asenapine and aripiprazole) in bipolar I disorder trials and schizophrenia maintenance trials were similar ([Pigott 2003; Keck 2006; Kane 2011; Szegedi 2018](#)). The cumulative relapse rate at Week 39 for the placebo group is assumed to be 35%, which is the average of the relapse rate in the placebo arm at Week 39 for the asenapine bipolar mania maintenance trial ([Kane 2011](#)) and the quetiapine bipolar I disorder maintenance trial ([Suppes 2009](#)).

Using these assumptions, the study would have to observe approximately 75 events to have 85% statistical power to detect that at least 1 dose is significant. The statistical method for the power calculation is based on the log-rank 2-sided test at the 5% significance level to compare the difference of each of the 2 survival curves of the cariprazine treatment groups versus that of placebo. Based on the assumed event rates, and considering the 26% of patients who may discontinue early from the study due to other reasons, approximately a total of 378 patients should be randomized to cariprazine 3.0 mg/d, cariprazine 1.5 mg/d, and placebo, or approximately 126 patients per treatment group.

It should be noted that this study is designed to test the 3.0 mg/d dose of cariprazine versus placebo first at the 0.05 significance level and, if the results are significant, then the 1.5 mg/d dose of cariprazine will be tested at the 0.05 significance level. Given this sequential testing strategy, the higher dose of 3.0 mg/d has 85% statistical power to show significance versus placebo, and the 1.5 mg/d dose, if it is as effective as the 3.0 mg/d dose, and the 3.0 mg/d dose is statistically significant, would also have 85% statistical power at the 0.05 significance level.

With the expectation that approximately 46% of patients will complete the OLTP period and will meet the randomization criteria, approximately 882 patients would be expected to enter and be treated with cariprazine in the OLTP.

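### Double-blind adverse events are shown by arm only as counts and percentages, although withdrawal at relapse shortens placebo follow-up by design; an exposure-adjusted display should be added as a supplement.

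*SAP*

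**What the plan says.** SAP 11.1 sets the main double-blind display: "The number and percentage of patients reporting TEAEs during the DBTP will be tabulated for each treatment group". Common TEAEs, serious TEAEs, EPS events and ocular events are also given as numbers and percentages, and AEs leading to discontinuation as an incidence. SAP 11.0 makes the double-blind safety population the denominator. AEs in the safety follow-up are tabulated separately. Protocol 7.3.4.1 follows the same pattern. Neither document specifies a rate per patient-year, a time-to-first-AE analysis or a cumulative-incidence curve for AEs.

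Protocol 8.9 lists among the mandatory reasons for discontinuation: "The patient meets the criteria for relapse of a mood episode during the DB treatment period". Time at risk for double-blind AEs therefore stops at relapse.

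SAP 9.1 already produces exposure by arm: "Patient-years will also be summarized by treatment group for the DBTP for the DB Safety Population". SAP Section 11 makes no reference to it.

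SAP 14.0 supplies the design assumptions: "The relapse HR is assumed to be 0.42"; "The cumulative relapse rate at Week 39 for the placebo group is assumed to be 35" percent; and sample size set by "considering the 26% of patients who may discontinue early from the study due to other reasons".

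**The concern.** A crude percentage compares arms fairly when patients are watched for similar lengths of time. Here they are not, and the imbalance grows with the drug's efficacy: the better it prevents relapse, the longer its patients stay at risk of an AE. Two arms with the same AE hazard would then show a higher percentage on cariprazine.

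Safety against placebo is part of both study objectives (SAP 5.0). A reader cannot remove the distortion from n (%) alone. Dividing by the total patient-years in SAP 9.1 is only a partial repair, because a count of patients with a given event needs person-time up to the first such event.

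**Working it through.** **Inputs (SAP 14.0).** Placebo relapse 35% at Week 39; hazard ratio 0.42; other dropout 26%; maximum follow-up 39 weeks; "log-rank 2-sided test at the 5% significance level"; 85% power; 126 per arm; about 75 events.

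**Reproducing the plan's own figures.**
- Cariprazine relapse risk: 1 − 0.65^0.42 = 16.6%.
- Pairwise events (Schoenfeld): 4 × (1.960 + 1.036)² / (ln 0.42)² = 47.7, so 48.
- Patients per arm: 48 / (0.35 + 0.1655) = 93.1; dividing by 0.74 gives 126, as stated.
- With exponential relapse and an independent 26% dropout over 39 weeks, observed relapse is 30.5% on placebo and 14.4% on cariprazine. Total events: 126 × (0.305 + 2 × 0.144) = 74.7, against the stated 75.

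The inputs therefore represent the plan faithfully.

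**Mean double-blind exposure.** Weekly hazards are:
- relapse on placebo: −ln(0.65)/39 = 0.01105
- relapse on cariprazine: 0.42 × 0.01105 = 0.00464
- dropout: −ln(0.74)/39 = 0.00772

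With h = relapse + dropout hazard, mean exposure = (1 − exp(−39h))/h.
- Placebo: h = 0.01877, giving 27.7 weeks.
- Cariprazine: h = 0.01236, giving 30.9 weeks.
- Ratio 1.12; about 67 and 75 patient-years per 126 patients.

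**Crude AE percentage under an equal, constant AE hazard g.** Percentage = g/(g + h) × (1 − exp(−39(g + h))).

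| AE risk over 39 weeks if all are followed | Placebo | Cariprazine | Ratio |
|---|---|---|---|
| 2% | 1.4% | 1.6% | 1.12 |
| 30% | 21.7% | 24.1% | 1.11 |
| 50% | 36.9% | 40.8% | 1.10 |
| 90% | 72.2% | 77.6% | 1.07 |

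In terms of observed placebo percentages, 10%, 20% and 30% appear as 11.2%, 22.2% and 33.2% on cariprazine.

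**Sensitivity of the exposure ratio**, which is close to the AE ratio for rare events:
- no dropout: 1.13
- 26% read as the crude observed dropout in each arm: 1.14
- relapse concentrated early (Weibull shape 0.6 to 0.8): 1.14 to 1.16
- relapse hazard rising over time (shape 1.3): 1.10 to 1.11

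Varying one assumption at a time, the inflation is about 7% (very common AEs) to 16% (rare AEs, early relapse).

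**Early-onset AEs.** Let the AE hazard g act only in the first W weeks, equally in both arms, with 20% risk by week W.
- Percentage = g/(g + h) × (1 − exp(−(g + h)W)).
- Mean person-time to first event = (1 − exp(−(g + h)W))/(g + h) + exp(−gW) × (exp(−hW) − exp(−39h))/h.

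| W | Placebo % | Cariprazine % | Crude ratio | Person-time, weeks (placebo; cariprazine) | Rate ratio |
|---|---|---|---|---|---|
| 4 | 19.3 | 19.5 | 1.01 | 22.5; 25.1 | 0.91 |
| 8 | 18.6 | 19.1 | 1.02 | 22.9; 25.5 | 0.92 |

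For such events the percentage is nearly unbiased. The rate per patient-year makes cariprazine look 8% to 9% better at equal risk, because its extra late event-free time dilutes the rate.

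**The case against.** The strongest objection is that a constant AE hazard is doubtful here. Randomized patients have already tolerated open-label cariprazine 3.0 mg/d; the earliest randomization visit is Week 12 (Protocol 3 and 4.6). New events may cluster after the switch. The percentage is then almost right and the rate is the more biased measure. This stands, and it rules out resting between-arm statements on the rate.

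The effect is also modest. Shifts of 1.2, 2.2 and 3.2 points at placebo percentages of 10%, 20% and 30% compare with standard errors √(2p(1 − p)/126) of about 3.8, 5.0 and 5.8 points, so each is under 0.6 standard errors. Safety is descriptive, with no between-arm AE test. Under the constant-hazard assumption the percentages overstate drug AEs, so they do not conceal harm. This stands too, as a limit on importance.

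The plan is not silent on exposure. Duration and patient-years appear by arm, and total TEAE counts by severity and relationship would allow a rough overall event rate. That shows the imbalance but does not adjust any patient-level AE figure.

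Some stronger readings are tempting but unsupported:
- A reader might infer from the hazard ratio (1/0.42 = 2.4) that relapse is assumed 2.4 times as frequent on placebo. That is the ratio of hazards; cumulative relapse is 35% against 16.6%, about 2.1 times.
- A reader might take 11% as a fixed inflation for both doses. SAP 14.0 gives the 1.5 mg/d dose the same effect only conditionally. If that dose prevents relapse less well, its exposure is closer to placebo and the inflation is smaller.
- A reader might conclude that no safety output will use patient-years. SAP 4.0 places table specifications in a separate document, so this can be said only of the SAP text.

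**Conclusion.** The point holds as a worthwhile, inexpensive improvement. The plan reports double-blind AEs by arm without any allowance for time at risk, while its own assumptions imply about 12% longer exposure on cariprazine. The resulting inflation of about 7% to 16% relative is a projection, not a figure in the documents. It requires an equal and roughly constant AE hazard, hazard ratio 0.42 in both dose arms, and dropout unrelated to AE risk. It falls to about 1% to 2% when events are confined to the first 4 to 8 weeks. Neither measure is right for every AE, so the percentages need a companion, not a substitute. The efficacy tests, type I error and sample size are untouched.

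**What to change.** In SAP 11.1, for the double-blind tables of any TEAE, common TEAEs, serious TEAEs, EPS TEAEs and AEs leading to discontinuation:
- Keep n (%) and add, by arm, patients with event per 100 patient-years at risk, with person-time counted to the first event or the end of double-blind exposure.
- For any TEAE and EPS TEAEs, add a time-to-first-event curve by arm with numbers at risk. This needs no constant-rate assumption. Estimate it as one minus Kaplan-Meier, censoring at relapse or other exit, and state the assumption that exit is unrelated to AE risk. Treating relapse and dropout as competing events would return essentially the crude percentages at Week 39 and adjust nothing.
- State that both displays supplement n (%) and are not the sole basis for between-arm statements, and that for early-onset AEs the rate can favour the longer-exposed arm (ratio about 0.91 to 0.92 at equal risk).

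The cost is extra columns in existing tables and two figures, from AE onset and dosing dates already collected. No endpoint, significance level, sample size or patient procedure changes.

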7.3.4.1 Adverse Events

AEs will be coded by system organ class and preferred term using the *Medical Dictionary for Regulatory Activities* (MedDRA), Version 21.0 or newer.

An AE will be considered a treatment-emergent adverse event (TEAE) if the AE began or worsened (increased in severity or became serious) on or after the first dose of OL IP.

The number and percentage of patients reporting TEAEs during the OL treatment period will be tabulated by system organ class and preferred term, by system organ class, preferred term, and severity, and by system organ class, preferred term, and relationship to IP.

The number and percentage of patients reporting TEAEs during the DB treatment will be tabulated for each treatment group by system organ class and preferred term, by system organ class, preferred term, and severity, and by system organ class, preferred term, and relationship to IP.

The number and percentage of patients reporting TEAEs during the SFU period will be tabulated by system organ class, preferred term, and DB treatment group for the DB safety population and by system organ class and preferred term for the OL safety follow-up population.

For the OL period, DB period, or SFU period, if more than 1 AE was coded to the same preferred term for the same patient, the patient will be counted only once for that preferred term using the most severe and most related occurrence for the summarization by severity and by relationship to IP.

The total number and percentage of TEAEs during the DB treatment period will also be summarized by severity and relationship to IP for each treatment group.

The number and percentage of patients with common ($\geq 2\%$ of patients in any treatment group) TEAEs during the DB period will be summarized by preferred term and treatment group.

An AE that occurs more than 30 days after the last dose of IP will not be summarized.

A SAE that occurred between the date of the first dose of IP and 30 days after the date of the last dose of IP, inclusive, will be considered an on-therapy SAE. The number and percentage of patients who had on-therapy SAEs during the OL period and the OL SFU will be summarized by preferred term. The number and percentage of patients who had on-therapy SAEs during the DB period and the DB SFU period will be summarized by preferred term and DB treatment group.

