6.2 OPEN-LABEL SAFETY POPULATION

The OL Safety Population will consist of all patients in the screened population who took at least 1 dose of OL cariprazine during the OLTP of the study.

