6.4 OPEN-LABEL SAFETY-FOLLOW-UP POPULATION

The OL SFU population will consist of patients in the OL safety population who were not randomized.

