6.5 RANDOMIZED POPULATION

The Randomized Population will consist of all patients in the OL Safety Population who were randomized to a treatment group during the DBTP of the study.

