11.0 SAFETY ANALYSES

The safety analyses will be performed for the OL safety, OL SFU and DB safety Population. The summarization will be overall for the OLTP in the OL safety population and OL SFU period in the OL SFU population, and by treatment group for the DB period and the DB SFU period in the DB safety population. The summarization for the OLTP will use the OL safety population as the denominator. The summarization for the DBTP will use the DB safety population as the denominator. The summarization for the OL SFU period or DB SFU period will use the OL SFU Safety Population or the DB safety population as the denominator respectively.

Safety parameters will include adverse events (AEs), clinical laboratory parameters, vital signs, Electrocardiogram (ECG) parameters, ophthalmology parameters, Columbia–Suicide Severity Rating Scale (C-SSRS), EPS scales, including Abnormal Involuntary Movement Scale (AIMS), Barnes Akathisia Rating Scale (BARS), and Simpson-Angus Scale (SAS), and prolactin level.

For each safety parameter, the last assessment made before the first dose of OL IP will be used as the baseline for all analyses of that safety parameter, unless stated otherwise. Continuous variables will be summarized by number of patients and mean, SD, median, minimum, and maximum values. Categorical variables will be summarized by number and percentage of patients.

The derived visits in the DBTP will use the same strategy as described in Section 10.0. The detailed week mapping windows is provided in Section 16.1.

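### The SAP names two different populations for the open-label safety follow-up TEAE table; the one in Section 11.1 would lower its percentages to about 0.54 of those on the protocol's denominator if followed literally

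*SAP*

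**What the plan says.** **The sentence at issue.** SAP 11.1 directs, with counts and percentages, that "patients reporting TEAEs during the OL SFU period will be tabulated by system organ class and preferred term for the OL Safety Population". SAP 6.2 defines the OL Safety Population as "all patients in the screened population who took at least 1 dose of OL cariprazine during the OLTP of the study". SAP 6.5 draws the Randomized Population from it: "all patients in the OL Safety Population who were randomized to a treatment group during the DBTP of the study". Randomised patients are therefore members of the population that 11.1 names.

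**The statements that differ.**
- SAP 6.4 sets up a separate population: "The OL SFU population will consist of patients in the OL safety population who were not randomized".
- SAP 11.0 gives the general rule on denominators: "The summarization for the OL SFU period or DB SFU period will use the OL SFU Safety Population" in the first case; in the second it names the DB safety population. The same paragraph also places the OL SFU summaries in the OL SFU population.
- The ocular-event paragraph of SAP 11.1 uses the OL SFU population for ocular TEAEs in this period.
- Protocol 7.3.4 makes the OL SFU population the denominator for the period. Protocol 7.3.4.1, on this very table, has it presented "by system organ class and preferred term for the OL safety follow-up population".

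SAP Section 18, which records departures from the protocol, lists the DB ITT definition and the age cut-off. It does not mention this table.

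**The concern.** A randomised patient's safety follow-up comes after double-blind treatment and is summarised as DB SFU on the DB safety population. Such a patient cannot contribute to the numerator of an OL SFU table. Putting these patients in the denominator lowers every percentage without changing any count.

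The table describes adverse events after open-label cariprazine is stopped in the patients who do not go on to randomisation, who are the larger part of the planned open-label cohort. If the 11.1 sentence were followed, three mismatches would arise:
- All-TEAE and ocular-TEAE percentages for the same period would rest on different denominators.
- The treatment-emergent SAE summary for the SFU period names no population, so it would presumably take the 11.0 rule and differ from the all-TEAE table.
- OL SFU percentages would be diluted while DB SFU percentages would not, which would mislead anyone reading the two side by side.

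**Working it through.** **Inputs**
- Planned number randomised: 378 (Protocol 4.1; SAP 14.0).
- Planned number entering open-label treatment: 822 (Protocol 4.1), but 882 (SAP 14.0).
- Expected share of open-label patients who are randomised: 46% (SAP 14.0).
- Planned number screened: 1245 (both documents). Screening failure: 34% (SAP 14.0).

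**Step 1: reproduce the planned open-label number.**
- From the randomised share: 378 / 0.46 = 821.7.
- From screening: 1245 × (1 − 0.34) = 821.7.

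Both routes give the protocol's 822. The SAP's 882 fits neither: 378 / 882 = 42.9% rather than 46%, and 882 / 0.66 = 1336 screened rather than 1245. I use 822 as the main figure and show 882 alongside because it is printed in the SAP.

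**Step 2: size of the OL SFU population.** By SAP 6.4 it is the open-label number minus the number randomised.
- 822 − 378 = 444
- 882 − 378 = 504

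**Step 3: dilution factor.** For a fixed number of patients with an event, the percentage on the OL Safety Population divided by the percentage on the OL SFU population is

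(N_OL − N_rand) / N_OL = 1 − N_rand / N_OL.

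- With 822: 444 / 822 = 0.54
- With 882: 504 / 882 = 0.57

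**Step 4: illustration.** Suppose 22 patients have a given event, a number chosen only as an example.

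| Planned open-label number | On OL SFU population | On OL Safety Population |
|---|---|---|
| 822 | 22/444 = 5.0% | 22/822 = 2.7% |
| 882 | 22/504 = 4.4% | 22/882 = 2.5% |

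**Step 5: dependence on the data.** The factor in the final report would be 1 minus the observed randomised fraction: 0.60 if 40% are randomised, 0.50 if 50% are.

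**Step 6: which statement is out of line.** The SAP's general rule, its ocular paragraph, and the protocol's general and table-specific rules all agree. Only the 11.1 TEAE sentence differs. The SAP amendment summary shows that the OL SFU population was introduced in Amendment #1 and the OL SFU TEAE summary in Amendment #2, so the right population was already defined when that summary was added.

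**The case against.** The strongest reply is that the plan, read as a whole, already gives the right answer. Section 11.0 is the only SAP text that uses the word denominator for this period, and it points to the OL SFU group. The protocol agrees in two places and no departure is declared. The SAP also says (Section 4.0) that table specifications are held in a separate document. That document is not available here and may settle the matter.

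Much of this stands. A reader might infer that the plan has settled on the OL Safety Population and that the reported rates will come out at about half the true ones. The documents do not support that, for two reasons:
- The dilution happens only if the 11.1 sentence is followed over 11.0 and the protocol, and nothing shows that it will be.
- A percentage on the OL SFU population is not strictly a true at-risk rate. SAP 6.4 includes every non-randomised open-label patient, while SAP 7.1 derives no SFU period for patients without follow-up visit assessments. It is the rate on the protocol-specified denominator and no more than that.

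The consequence is also limited. This is one descriptive, single-group table with no hypothesis test, and SAEs, including those in follow-up, are listed separately for the Screened Population.

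The reply does not remove the contradiction. The 11.1 sentence is the more specific instruction for this table, and the SAP does not say whether a general or a specific statement prevails. Section 11.0 is not clean either: it refers to an OL SFU Safety Population, a name that Section 6 does not define.

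**Conclusion.** The contradiction is real and should be corrected before the table is produced. SAP 11.1 conflicts with SAP 11.0, with its own ocular paragraph and with Protocol 7.3.4 and 7.3.4.1, and Section 18 does not declare the difference.

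The numerical effect is conditional. If 11.1 is taken literally, this table's percentages fall to about 0.54 of their value on the protocol's denominator, or 0.57 on the SAP's open-label figure. Both factors assume the planned numbers. If 11.0 and the protocol are followed, there is no effect. Confidence is high that the wording conflicts; whether the wrong table would be produced cannot be determined from these documents.

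**What to change.** 1. In SAP 11.1, name the OL SFU population instead of the OL Safety Population for TEAEs in the OL SFU period.
2. In SAP 11.0, replace the undefined OL SFU Safety Population with the name given in Section 6.4.
3. Check the separate table specifications against both sections, so that the all-TEAE, treatment-emergent SAE and ocular tables for this period share one denominator.

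The cost is a few words and one check of the specifications. No data or analysis is added. No entry in Section 18 is needed, because the change restores agreement with the protocol.
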